HIAS will promote the incubation of businesses through its Entrepreneurship School with Gender Lens (ESGL), a methodology that targets GBV survivors and women at-risk to help them develop business ideas, access needed support for the prevention of and response to GBV, exploitation and trafficking, and improve participants' overall self-reliance. Participants will go through a general business curriculum, work on business plans and learn gender issues and ways to mitigate GBV risks. Upon training completion, participants are eligible to pitch their business idea to a panel of experts and receive \$800 of seed capital. They will also receive follow-up business advisory support for at least six months, focusing on access to markets and finance and building support networks, in order to continue building self-reliance.

The ESGL will include a mental health and psychosocial support module, contributing to participant self-sufficiency, resilience, and empowerment through skills development such as coping skills, problem-solving capabilities, self-esteem, self-efficacy, communication abilities, self-regulation, and leadership, aimed at strengthening their ability to generate dignified livelihoods.

Study objective

This study will conduct a pilot-randomised controlled trial to evaluate the entrepreneurship curriculum. The evaluation has three primary objectives:

1. Evaluate the preliminary effectiveness of the entrepreneurship programming to improve household self-reliance, mental health, and empowerment for households where women members run businesses.
2. Examine the relationship between GBV risk and self-reliance among women refugees in the Colombian migration context.
3. Assess the feasibility and acceptability of the refugee self-reliance index as a measurement tool in programs that strengthen self-reliance pathways for women individuals.

Methodology

Overview

This pilot RCT will be conducted in Cali, Ipiales, Pasto, and Popayan, and will include a control group. Eligible participants will be randomized to the treatment or control arm and the study team will collect data from both the intervention and comparison groups at: 1) the program baseline, 2) the program endline (8 months post-baseline), and 3) follow-up 3-4 months after program completion.

Screening for Eligibility: Inclusion Criteria

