Participants will be recruited from four cities: Cali, Ipiales, Pasto, and Popayan. The study will aim to enrol 80 women in the study within each city, where participants will be randomly assigned to the intervention or control arm at a 2:1 ratio.. As such, 90-100 women will be identified as potential participants through the pre-screening tool to account for ineligibility during the SRI administration phase.

At the time of enrolment, participants will receive a unique study ID. Following enrolment and baseline data collection, participants will be randomly assigned to the control or treatment arm using a random number generator in Stata (a data analysis software). The unique study ID will be used to track participants over time for future points of data collection.

Consent

Prior to data collection, the researcher will explain the study purpose, procedures, potential risks, and safeguards, such as participant confidentiality and referrals for services, where necessary. The researcher will explain that participants may be assigned to take part in the intervention based on randomization but that non-selection for the intervention will not prevent them from later participation in HIAS programs. They will be informed that they may also be provided with a referral for other programs. The researcher will emphasize that participation is completely voluntary and that participants will not be penalized in any way for choosing not to participate. Researchers will also explain and emphasize that participating or not participating in the study is purely voluntary and will have no impact on their access to future HIAS programming. Prospective participants will also be told that they are free to withdraw from the study at any time and to refuse to answer some or all of the questions. Participants will be informed that their data may be used by the research team in the future. The researcher will encourage the interviewee to ask any questions about the study processes before consenting to participate in the study.

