The Self-Reliance Index (SRI) is the first-ever global tool for measuring the progress of refugee households toward self-reliance (Seff, Leeson, and Stark, 2021). The tool contains twelve domains focused on a household's basic needs, resources, and sustainability. Domains measure conditions and assets that increase the likelihood that refugees will be able to continue meeting their needs in the future. The study participant will respond on behalf of her household. The final self-reliance score may take a value from 1 to 5, with higher scores reflecting greater self-reliance. The tool is available in Spanish and has been previously validated with Venezuelan migrants in Colombia.

Resilience:

The Brief Resilient Coping Scale (BRCS) captures tendencies to cope adaptively with stress. The scale focuses on the tendency to effectively use coping strategies in a flexible and committed manner to actively solve problems despite stressful circumstances (Trejos Herrera et al., 2023).

Women's empowerment

Women's empowerment will be measured using the Women's Multidimensional Empowerment Index, which was developed using the 2015 Colombian Demographic and Health Survey (Rodríguez Guerrero, Nimeh, & Franco Correa, 2021). The index assesses empowerment multidimensionally based on the definition of empowerment proposed by Kabeer (1999) (Resources, domestic decision making, decision making on personal matters, and achievements), while capturing the notion of disempowerment.

Gender-based violence: Three items from the HIAS Knowledge and Perception of GBV risks and Women's Empowerment tool will be used. The HIAS tool was adapted based on other tools used in the Latin American region (cite). The three items pertain to self-reported perceptions of feeling supported by the community, feeling useful, and feeling controlled by one or more people. Responses are on a likert scale.

Ethical considerations

Risks and Benefits

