## 1. Objectives

- To assess the impact of the ESGL intervention on household self-reliance, depressive symptoms, and resilience.
- To estimate both the intent-to-treat (ITT) and the local average treatment effect (LATE) of the intervention using instrumental variable analysis.
- To explore the role of participant characteristics in loss to follow-up and outcome changes.

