## 2. Primary Outcomes

- Self-reliance: Total and domain-specific scores from the Self-Reliance Index (SRI), with scores ranging from 1 to 5 (except health status domain: 1–3).
- Depression: Patient Health Questionnaire-9 (PHQ-9), scores range 0–27; higher scores indicate more severe depressive symptoms.
- Resilience: Brief Resilient Coping Scale (BRCS), scores range 4–20; higher scores indicate greater coping ability.

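### The SRI is a household score, but women are enrolled and randomised one by one with no one-per-household rule, so a control woman's score may reflect a housemate's treatment

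*Protocol*

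**What the plan says.** **Outcome level.** The Protocol describes the SRI as a household tool: "The tool contains twelve domains focused on a household's basic needs, resources, and sustainability". It adds: "The study participant will respond on behalf of her household". Its first objective is to "improve household self-reliance, mental health, and empowerment for households where women members run businesses". The first objective in SAP section 1 is "To assess the impact of the ESGL intervention on household self-reliance, depressive symptoms, and resilience". SAP section 2 lists the SRI, the PHQ-9 and the BRCS as primary outcomes without ranking them, and the SRI entry covers both total and domain scores.

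**Enrolment and allocation.** Apart from the SRI score itself, every eligibility criterion (Protocol, Screening for Eligibility; SAP section 3) describes the individual woman. Under Subject Recruitment the Protocol says "participants will be randomly assigned to the intervention or control arm at a 2:1 ratio". Each woman receives her own study ID, and no household ID is mentioned.

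**Intervention.** After training, "participants are eligible to pitch their business idea to a panel of experts and receive" $800 of seed capital, followed by at least six months of business advice.

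**Analysis.** The OLS and 2SLS models (SAP sections 5.1 and 5.2), the attrition analysis (section 6) and the sensitivity analysis (section 7) contain nothing about shared households. The Protocol's random coefficient models have random effects for the participant only.

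**The concern.** The outcome belongs to the household and the allocation belongs to the woman. Women are drawn within a city from one organisation's database, and the SRI eligibility range screens on a household construct, so two women from one home could both qualify. Each would then be randomised separately.

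If one is treated and the other is a control, the control woman answers for a household that may have gained seed capital and business income. Her score enters the control mean, and the contrast between arms on the SRI may be diluted.

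The 2SLS analysis does not repair this. SAP section 5.2 defines adherence by the woman's own certificate and seed capital, so the control woman is correctly coded as non-adherent and her housemate's treatment appears nowhere in the model. The usual assumption that one participant's assignment does not affect another's outcome then fails for both the ITT and the LATE.

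**Working it through.** The documents give no power calculation or expected effect, so there is no stated figure to reproduce.

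**Inputs from the documents**
- Allocation 2:1 and 80 women per city (Protocol).
- Four cities in the Protocol, giving N = 4 × 80 = 320. The SAP says three cities; at the Protocol's 80 per city that gives N = 3 × 80 = 240.

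**Assumptions**
- q, the share of enrolled women who live with one other enrolled woman, is not given. Values from 2% to 20% are shown.
- For power only: two-sided alpha 0.05, no dropout, and 80% power when q = 0. This corresponds to a detectable difference of 0.33 SD at N = 320 or 0.38 SD at N = 240.

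**Step 1: how often pairs are split.** With independent 2:1 allocation, P(split) = 2 × (2/3) × (1/3) = 4/9 = 44.4%. With fixed 53:27 allocation of 80, it is 2 × 53 × 27 / (80 × 79) = 45.3%. A control woman in a pair has a treated housemate with probability of about 2/3. So does a treated woman in a pair.

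**Step 2: effect on the ITT contrast.** Let δ be the household effect of one treated member. Let s be the share of δ that a control housemate's score picks up, and r the extra share of δ when a second member is treated.
- Treated mean shift: δ[1 + (2/3)qr]
- Control mean shift: δ(2/3)qs
- Contrast: δ[1 − (2/3)q(s − r)]

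With s = 1 and r = 0, the contrast is δ[1 − (2/3)q]. With s = r = 1 (effects add up), it is δ, with no dilution. Partial spillover (s below 1, with r = 0) gives something between these.

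**Step 3: numbers for s = 1, r = 0.** Split pairs = (qN/2) × 4/9.

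| q | Shrinkage (2/3)q | Split pairs, N = 320 | Split pairs, N = 240 | Power, from an assumed 80% |
|---|---|---|---|---|
| 2% | 1.3% | 1.4 | 1.1 | 78.9% |
| 5% | 3.3% | 3.6 | 2.7 | 77.3% |
| 10% | 6.7% | 7.1 | 5.3 | 74.4% |
| 20% | 13.3% | 14.2 | 10.7 | 68.0% |

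**Step 4: 2SLS.** With assignment as the only instrument and no covariates, the estimate is the ITT contrast divided by the difference in adherence between arms. A housemate's treatment does not alter how adherence is coded, so the denominator is unchanged and the estimate shrinks by the same proportion as the ITT.

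**Step 5: standard errors.** In the difference in means, each treated woman has weight 3/(2N) and each control woman 3/N. In units of 1/N², the within-pair covariance term carries the factor 9/4 for a treated pair, 9 for a control pair and −9/2 for a split pair. The expected sum is (4/9)(9/4) + (1/9)(9) − (4/9)(9/2) = 1 + 1 − 2 = 0. A simulation agrees: with N = 240 (160:80), identical scores within pairs, no effect and 20,000 runs, the unclustered test had type I error of 5.1% at q = 10% and 4.7% at q = 30%.

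**The case against.** The strongest reply is that nothing in the documents shows that any two enrolled women share a home. Each must separately have an entrepreneur profile, be at risk of or have experienced GBV, and have an SRI score in range, which narrows the chance. At 2% to 5% sharing the worst case is a loss of 1.3% to 3.3%, small in a pilot of preliminary effectiveness. Dilution also depends on how household effects combine: if a second treated member adds as much as the first, both arm means rise equally and the contrast is intact. All of this stands. It limits the size of the point but does not close the gap, because as written nobody can tell whether sharing is rare.

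A reader might infer more than the documents support:

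- **That same-arm pairs make the standard errors too small, so errors should be clustered on household.** Under individual randomisation the same-arm and split-pair terms cancel (step 5), so this does not hold.
- **That dilution is established.** It is conditional on q, s and r, none of which is given.
- **That housemates must record identical scores or pass the SRI range together.** They share a construct but answer separately, so their scores can differ.
- **That the $800 is paid to the household.** It is seed capital for the woman's business, conditional on completing training and pitching. That it reaches the household is an inference, though an effect on a household score largely depends on it.
- **That all primary outcomes are affected.** The PHQ-9 and BRCS are individual scores, and the calculation does not extend to them.

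**Conclusion.** The mismatch between a household outcome and individual allocation is in the text, and no enrolment rule, identifier or model term addresses it. The consequence is possible interference on the SRI, in both the ITT and the 2SLS estimates. The ITT effect shrinks by up to (2/3)q: 1.3%, 3.3% and 6.7% at q = 2%, 5% and 10%. That upper limit requires the household to gain the full effect from one treated member and nothing from a second. If effects add up, there is no dilution. Because the co-residence rate is unknown, the point is minor to moderate. It is worth acting on mainly because prevention or measurement is cheap.

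**What to change.** **If enrolment is open.** Add to the Protocol's inclusion criteria and SAP section 3 that only one woman per household may be enrolled, chosen at random if several qualify. This costs one sentence and a check at pre-screening; the downside is that a few eligible co-resident women are not enrolled. The alternative is to randomise the household. That keeps those women but always puts them in the same arm, so the SRI analysis would then have to treat the household as the unit.

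**If randomisation is complete,** as the past tense in SAP section 3 suggests:
1. Identify from baseline data the households with more than one participant. The documents do not say whether addresses or other linking data are held.
2. Report how many such households there are and how many are split between arms.
3. Add to SAP section 7 a repeat of the SRI ITT and 2SLS analyses that excludes every household with more than one participant.

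The exclusion must not be limited to split households. Being split is a result of randomisation: removing only those would drop about 1/3 of paired treated women but 2/3 of paired controls, and would leave only same-arm pairs. Sharing a household at baseline precedes allocation, so excluding on it keeps the comparison randomised. The cost is one linkage check, one sensitivity run and the loss of a share q of the sample in that run.

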Using their database and a pre-screening tool, HIAS will identify potential participants who meet the following criteria: women, at least 18 years of age, at risk of GBV or ever experienced GBV, have a migratory permit (for migrants and refugees), are Colombian or Venezuelan, have been residing in Colombia for at least six months, and have an entrepreneur profile registered with HIAS. Individuals with the targeted characteristics will then be further screened for study eligibility using the Self-Reliance Index (SRI). First launched in 2020, the Self-Reliance Index (SRI) is the first-ever global tool for measuring the progress of refugee households toward self-reliance (Seff, Leeson, and Stark, 2021). Eligible participants must receive a score between 2 and 3.5 on the tool to be included in the study. This range of scores aims to capture women who are vulnerable, but who are in a stable enough situation to develop an income generating activity (meaning that they are not unhoused or in need of urgent humanitarian assistance), while still in need of financial support, training and GBV assistance. If a participant's score on the SRI falls outside of the specified range, they will be ineligible for further inclusion, thanked for their time, and removed from the study. Participants whose score falls within the specified range will be included in the study and further baseline data will be collected including information on mental health, empowerment, and safety.

Subject Recruitment, enrolment and sample size

HIAS will use their database and the pre-screening tool to identify potentially eligible participants for the study. They will aim to identify approximately 90-100 potentially eligible women through

the pre-screening tool. Official enrollment, consenting, and formal assessment of eligibility will be carried out by the research team. Data collectors will obtain written consent from previously pre-screened women prior to administering the SRI. After administering the SRI, data collectors will immediately administer the remaining survey questionnaire modules for participants whose SRI scores fall within the eligible range of 2 to 3.5. Women whose scores fall outside of the 2-3.5 range will be thanked for their time and not assigned to an evaluation arm.

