According to Resolution number 008430 of 1993 of the Colombian Ministry of Health and Social Protection, this is "research without risk", which includes: "studies that employ retrospective documentary research techniques and methods and those in which no intervention or intentional modification of the biological, physiological, psychological or social variables of the individuals participating in the study is carried out, including: review of medical records, interviews, questionnaires and others in which no sensitive aspects of their behaviour are identified or dealt with".

The study is expected to carry minimal risk of loss of confidentiality associated with participation in group discussions, which will be minimized by data confidentiality measures and by using verbal informed consent procedures. Individuals have the option to not participate, or if they choose to participate, to decline to answer any question that they do not feel comfortable answering, or to choose to end their participation in the study at any time. We do not anticipate any psychological risk that may result from study participants. All measures will be taken to minimize the risk related to the contracting and spreading COVID-19 among any of the researchers or study participants, following the guidelines of the Ministry of Health and the University.

Safety and Adverse Events

All referral processes will be handled by HIAS as follows.

CASE MANAGEMENT PROTOCOL AND REFERRAL ROUTES

At HIAS, we have developed clear pathways and procedures to prevent, identify, and promptly address the needs of all Persons of Concern (PDI), that is, all participants who are directly or indirectly involved with each of our programs. For HIAS Colombia, it is essential to meet the needs of our beneficiaries, especially those who will be part of the Owning Rights and Protection: GBV Prevention, Mitigation, and Response in Colombia project.

This protocol was created to specify the pathways for care and management of cases and needs that may arise during the implementation of the research and that, in turn, represent a risk to the psychosocial well-being and safety of our participants and their families. For example, cases of PDI who are not selected to participate in the EGV, participants who have been randomly assigned to the control group, and/or participants who receive EGV training and express some type of need for care.

STEPS FOR CASE MANAGEMENT AND REFERRAL ROUTES

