- IE Officers and Research Assistants who will be present at the training and data collection spaces will be trained to address any type of situation or need by providing crisis support and Psychological First Aid to individuals experiencing emotional distress, family conflicts, domestic violence, and suicidal thoughts.
- IE Officers will then inform the IDPs about the services available at HIAS (GBV Case Management, Individual Psychosocial Care, and Legal Protection) and will ask each individual if they would like to be referred to any of these services.

Stage 3. Recording the Situation or Need

When participants express a need to be assisted by HIAS professionals, the needs and/or situation assessment process is activated.

Likewise, the following actions will be carried out:

- Internal referral forms will be used to describe the identified situation, the level of risk identified, the priority range under which the case should be addressed, and whether the participant's consent is obtained.
- Once the PDI's consent is obtained, the IE Officer will carry out the referral process to the GBV Case Manager or the MHPSS Officer, using the internal case referral forms provided by the MHPSS and GBV department.
- The MHPSS and GBV services at HIAS Colombia conduct risk and needs assessments to determine the support participants require, as well as to negotiate access to additional services with partner organizations. Should external referrals arise, the GBV Case Manager or the MHPSS Officer will be responsible for making them and following up on them.
- The Economic Inclusion Officer will follow up on referrals and will be in contact with the MHPSS Officer or GBV Manager in charge of providing care to the beneficiary.

HIAS Colombia has developed a matrix of physical and psychosocial risks associated with the implementation of the gender-responsive entrepreneurship school program, and has also implemented risk mitigation actions for each situation.

Stage 4. Response to the situation that occurred or need encountered

4. Respuesta a la situación ocurrida o necesidad encontrada

- Cualquier situación de riesgo o necesidad será canalizada por el Oficial de Inclusión Económica, quien deberá remitir a los Oficiales SMAPS y Gestor de casos VBG según se requiera.
- Los asistentes de investigación deberán comunicar de manera inmediata al Oficial de Inclusión Económica sobre la situación y este deberá activar la ruta interna de remisión correspondiente.

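### The protocol's no-risk classification contradicts its own description of the trial; separately, the SAP plans no by-arm summary of GBV-related harm

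*Protocol*

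**What the plan says.** **Risk classification.** Protocol, Risks and Benefits, adopts a national no-risk category and quotes its definition. The category is for studies in which "no intervention or intentional modification of the biological, physiological, psychological or social variables of the individuals participating in the study is carried out". Its examples are "review of medical records, interviews, questionnaires and others in which no sensitive aspects of their behaviour are identified or dealt with". The section then states: "We do not anticipate any psychological risk that may result from study participants". The ethics form at the end of the protocol (Ethical Considerations) repeats the classification and that sentence.

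**What the trial does.** Under Subject Recruitment, "participants will be randomly assigned to the control or treatment arm using a random number generator in Stata". Under Intervention, "The ESGL will include a mental health and psychosocial support module, contributing to participant self-sufficiency, resilience, and empowerment". Women who complete training may pitch a business idea and receive $800 of seed capital. Eligibility requires past experience of GBV or being at risk of it.

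**What risks the protocol expects.** Safety and Adverse Events sets out case management for situations in the research that threaten participants' well-being and safety, and names control-arm women among those covered. Stage 3 states: "HIAS Colombia has developed a matrix of physical and psychosocial risks associated with the implementation of the gender-responsive entrepreneurship school program". Stage 4 refers to committees that review continued participation when GBV-risk incidents occur during the programme.

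**What is analysed.** The protocol summary lists GBV risk among the outcomes of interest. Its GBV measure is three perception items, one of which is about feeling controlled by one or more people. SAP section 2 lists the Self-Reliance Index, PHQ-9 and the Brief Resilient Coping Scale. SAP section 5.1 compares change in each outcome by assigned arm. The SAP contains no safety or harms section and no GBV item.

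**The concern.** There are two separate problems.

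First, the risk statements are wrong for this design. An ethics committee reading them is told that the study modifies nothing psychological or social and touches no sensitive topic. The rest of the protocol says otherwise.

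Second, the harm most specific to this population is a rise in control or violence once a woman is in a programme that provides money. The SAP would give no by-arm result on it. Mean change in PHQ-9 is compared, but an average improvement is compatible with some women getting worse, and PHQ-9 does not measure control by others. The trial could therefore report its effects on self-reliance, depression and resilience with nothing to say on GBV risk, which the protocol names as an outcome and makes part of its second study objective.

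**Working it through.** **Step 1: the no-risk definition against the design.**

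| Condition for the category | What the protocol describes |
|---|---|
| No intervention on, or deliberate change to, psychological or social variables | Random assignment by the study team; a psychosocial module aimed at coping, self-esteem and self-efficacy; seed capital (Subject Recruitment; Intervention) |
| No sensitive aspects of behaviour | Participants selected on GBV experience or risk; baseline data on mental health and safety; an item on feeling controlled (Screening; Study Outcome Measures) |

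Neither condition is met.

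**Step 2: the sentence anticipating no psychological risk against the safety text.** The protocol expects cases that threaten psychosocial well-being and safety (Safety and Adverse Events). It trains staff to support women with distress, domestic violence or suicidal thoughts (Stage 2). It cites a matrix of physical and psychosocial risks tied to the programme (Stage 3) and incident-review committees (Stage 4). These cannot all stand beside that sentence.

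**Step 3: what the SAP compares by arm.** PHQ-9 change is compared (sections 2 and 5.1). The item on feeling controlled is not mentioned. Adverse events, GBV incidents and referrals are not mentioned either, and the protocol's own safety section describes referral procedures without any summary by arm.

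**Step 4: what a by-arm table could show.** The documents give no harm rate, power or sample-size calculation, so there is no stated figure to reproduce.

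Inputs from the documents:
- 80 women per city, allocated 2:1 (Protocol).
- Four cities (Protocol) or three (SAP section 3).

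Assumptions:
- 80 per city still applies with three cities.
- The share of women who worsen is p in both arms.
- Loss to follow-up is 0% or 20%, equal in both arms.

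Arm sizes: 4 × 80 = 320, about 213 and 107; 3 × 80 = 240, that is 160 and 80.

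95% CI half-width for the risk difference = 1.96 × √[p(1 − p)(1/n₁ + 1/n₀)].

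- N = 320, p = 0.20: 1.96 × √[0.16 × (1/213 + 1/107)] = 0.093.
- N = 240, p = 0.20: 1.96 × √[0.16 × (1/160 + 1/80)] = 0.107.
- With 20% loss, divide by √0.8: 0.104 and 0.120.

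| p (assumed) | N = 320, no loss | N = 320, 20% loss | N = 240, no loss | N = 240, 20% loss |
|---|---|---|---|---|
| 10% | ±7.0 | ±7.8 | ±8.1 | ±9.0 |
| 20% | ±9.3 | ±10.4 | ±10.7 | ±12.0 |
| 30% | ±10.6 | ±11.9 | ±12.3 | ±13.8 |

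(percentage points)

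For scale, take a 20% control rate, no loss, two-sided α of 0.05 and 80% power (both assumed), with the usual two-proportion formula using pooled variance under the null. The treatment-arm rate would have to reach about 34.9% (N = 320) or 37.5% (N = 240), a rise of about 15 to 17.5 points.

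**The case against.** **The label may cover only the surveys, with the implementing organisation delivering the programme.** This does not rescue the statement. Random assignment to the programme is a research procedure, and the surveys themselves ask about sensitive matters.

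**The protocol does take safety seriously.** It has a referral pathway, a risk matrix with mitigation, and incident review. That is true. It is also why a reader should not infer that the SAP lacks a harms table *because* no risk was recognised. No text makes that link, and the two gaps stand separately.

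**Harms are compared, through PHQ-9.** This stands in part. It would be wrong to say that harms are never compared between arms: mean PHQ-9 change is a primary comparison and could show worsening. What is missing is narrower, namely GBV-related harm and the share of women who worsen.

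**The items may not be available together.** This stands. PHQ-9 is not in the protocol's list of measures, and the item on feeling controlled is not in the SAP. No single document lists both, so one cannot assume that both were collected at every round. The item also refers to control by any person, not specifically a partner.

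**A worsening share can mislead too.** This stands as a limit. If most treated women improve, the treated share that worsens may fall even though some women were harmed, and without a set threshold a one-point PHQ-9 rise would count as harm. The table is descriptive and needs that threshold in advance.

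**Two consent readings are tempting but unsupported.** One is that the consent form carries the same risk wording. The form is not available for review, and the Consent section says potential risks are explained. The other is that verbal consent in the risk paragraph conflicts with the statement that "Data collectors will obtain written consent from previously pre-screened women prior to administering the SRI". The verbal procedure is mentioned alongside group discussions and may apply only to those.

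**Conclusion.** The contradiction in the risk statements is established from the protocol's own text and rests on no assumption. The classification and the sentence anticipating no psychological risk are wrong as written, in both places where they appear.

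The analysis gap is real but limited. The SAP compares mean PHQ-9 change by arm; it plans nothing by arm on GBV-related harm and leaves out the protocol's nearest measure of it. Adding that comparison would be worthwhile but imprecise. At an assumed 20% worsening rate the half-width is about 9.3 to 10.7 points without attrition and about 10.4 to 12.0 with an assumed 20% loss. The lower figure in each pair is for 320 women and the higher for 240. A modest increase in harm would be neither detected nor ruled out. The worsening rates, the loss and the three-city total are assumptions.

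**What to change.** 1. **Protocol, Risks and Benefits, and the ethics form.** Remove or correct the no-risk classification and the sentence anticipating no psychological risk, so that they agree with the Intervention, Safety and Adverse Events, and Stage 3 and 4 text. Notify the ethics committee so that it can assign a category that fits an intervention trial. The SAP describes randomisation in the past tense, so this may have to be a corrective notice.

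2. **SAP.** Add a descriptive comparison by assigned arm, at each follow-up round where the items were asked. Report change in the item on feeling controlled, and the share of women who worsened on that item and on PHQ-9. Set the worsening thresholds before the comparison is run, and give risk differences with 95% CIs. Use the interview items, not referral forms. Officers and research assistants present at training sessions may see treatment-arm women more often, so referral counts could differ by arm for that reason alone. State which items were collected at which round.

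**Cost.** Revised wording, one ethics amendment or notice, and one table. The downside is a less favourable risk statement and wide intervals that must be reported as such.
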